APPENDIX B. SPECIMEN SAMPLING AND HANDLING

Pharmacokinetic Serum Collection and Processing Instructions	
Venipuncture and transfer tube label information	Study number, subject randomization number, sample type (eg, PK), study period (if applicable), nominal collection time, sample set (A or B)
Sample processing (serum)	
 1. Collect samples (approximately 5 mL) into Vacutainer® tubes (tube red top, 13 x 75 mm, silicone coated interior) containing no anticoagulant 2. Immediately after the sample is drawn, gently invert the tube 5 times. Allow tubes to sit at room temperature for at least 20 minutes (no more than 40 minutes) 3. Centrifuge ~10-15 minutes (at room temperature at 2500 to 3000 rpm [approximately 650 to 1450 x g]) to achieve a clear serum layer over the clotted red cells (the speed and time may be varied according to the make and model of centrifuge used) 4. Transfer approximately equal portions of separated serum (at least 1 mL) into 2 labeled, polypropylene transfer tubes (sets A and B)
Storage	Samples will be stored at a temperature of –20°C in an upright position until they are shipped to the bioanalytical laboratory. For every MPA blood draw, batch one aliquot (“aliquot 1”) for eventual shipment to PPD store, and one aliquot (“aliquot 2”) to be stored on site during the study as back up in case additional testing is needed.
Shipping	The bioanalytical laboratory will be notified prior to the shipment of the samples. Primary and backup samples are not to be sent in the same shipment. An electronic file containing sample collection dates will be emailed to the bioanalytical laboratory and the sponsor’s bioanalytical department representative for each shipment.

Statistical Analysis Plan Version 5.0

Pharmacokinetics Study–Healthy Subjects

Study TV46046-WH-10159

INTRODUCTION

This Statistical Analysis Plan (SAP) describes the planned analysis for *A Randomized, Dose-range Finding Study to Evaluate Pharmacokinetics of Medroxyprogesterone Acetate Following a Single Subcutaneous Administration of TV-46046 in Healthy Women of Reproductive Age*. The study is sponsored by Teva Branded Pharmaceutical Products R&D, Inc. and is implemented by FHI 360.

The reader of this SAP is encouraged to read the protocol for details on the conduct of this study, the operational aspects of clinical assessments, and the timing for completing the participation of a subject in this study. Version 1.0 of the SAP expands upon the analysis of primary and secondary endpoints outlined in Protocol Amendment 01 (the current version at the time of first subject enrolled), including definitions of estimands and methods for handling missing data and intercurrent events. When differences exist in descriptions or explanations provided in the study protocol and this Statistical Analysis Plan, the SAP prevails; any such differences will be explained in the Clinical Study Report (CSR).

Future changes to the SAP (e.g., to address amendments to the protocol) and their temporal relationship to unblinding will be documented in Section 12 and detailed in the CSR. Mock tables, figures and listings will be approved by the Coordinating Investigator prior to un-blinding of study statisticians and maintained in a separate document.

1. STUDY OBJECTIVES AND ENDPOINTS

The overall goal of this study is to select a dose of TV-46046 (medroxyprogesterone acetate [MPA] injectable suspension 300 mg/mL) that is safe, well tolerated, and has a pharmacokinetics profile consistent with contraceptive protection when injected every 6 months.

1.1. Primary Study Objective and Endpoints

1.1.1. Primary Objective

The primary objective of this study is to evaluate and compare the pharmacokinetics profile of MPA following subcutaneous administration of 3 doses of TV-46046 300 mg/mL (120 mg/0.4mL; 180 mg/0.6mL; 240 mg/0.8mL), and 104 mg/0.65 mL Depo-subQ Provera 104 in healthy female subjects.

1.1.2. Primary Endpoints

The following non-exhaustive list of pharmacokinetics parameters will be evaluated to support the primary objective of the study:

- C_{\max} (maximum observed serum concentration)
- T_{\max} (time to C_{\max})
- Serum MPA concentrations at treatment days 91, 182, and 210 (C_{91} , C_{182} , C_{210})
- AUC_{0-182} (area under the serum drug concentration-time curve from time 0 to day 182)
- AUC_{0-210} (area under the serum drug concentration-time curve from time 0 to day 210)
- $AUC_{0-\infty}$ (area under the serum drug concentration-time curve extrapolated to infinity)
- Apparent terminal half-life ($t_{1/2}$)

1.2. Secondary Study Objectives and Endpoints

1.2.1. Secondary Objectives

The secondary objectives of the study are:

- 1) to evaluate and compare the safety and local tolerability of a subcutaneous injection of 3 doses of TV-46046 300 mg/mL (120 mg/0.4mL; 180 mg/0.6mL; 240 mg/0.8mL) and Depo-subQ Provera 104 in healthy female subjects
- 2) to evaluate the acceptability of a subcutaneous injection of TV-46046 over the range of different doses

Statistical Analysis Plan Version 5.0

Pharmacokinetics Study–Healthy Subjects

Study TV46046-WH-10159

1.2.2. Secondary Endpoints

The safety and local tolerability measures/parameters are:

- occurrence of adverse events
- use of concomitant medication
- vital signs
- body weight measurement
- vaginal bleeding pattern
- assessment of mood by Patient Health Questionnaire-9 (PHQ-9)
- liver function tests
- estradiol (E2) measurements throughout the study
- progesterone (P) measurements at Weeks 48, 49, 50, 51, and 52
- occurrence of injection site reactions (ISRs)
- subjects' responses to acceptability questions

2. STUDY DESIGN

2.1. General Design

This is a randomized, partially-blinded dose-range finding study to evaluate and compare the pharmacokinetics, safety, local tolerability, and acceptability of the subcutaneous administration of 3 different doses of TV-46046 300 mg/mL (120 mg/0.4 mL, 180 mg/0.6 mL, or 240 mg/0.8 mL) and the reference product Depo-subQ Provera 104 (104 mg/0.65mL) in healthy female subjects.

Study procedures and their timing in relation to treatment initiation are summarized in Table 1 of the protocol.¹ Briefly, study participation will consist of a screening period, treatment initiation and 52 weeks of primary follow-up. Enrolled subjects will provide blood samples for MPA testing at baseline (Day 0, prior to injection of study drug); Day 1, 2, 3, 5, 7, 10, 12, 14, 18, 21, and 28 post-injection; and Week 6, 8, 10, 12, 13, 15, 17, 19, 21, 23, 25, 26, 28, 30, 32, 36, 40, 44, 48, and 52 post-injection. Specimens for P and E2 measurement will be collected at Day 0 and Weeks 48, 49, 50, 51 and 52, and specimens for E2 measurement will be collected at all visits where samples for MPA or P are taken starting on Day 28.

Subjects will be evaluated for vital signs, body weight, liver enzymes, and ISRs at Weeks 1, 13, 26, and 52 post-injection; vaginal bleeding patterns will be assessed at Weeks 13, 26, and 52; acceptability will be assessed at Weeks 26 and 52; and mood will be evaluated on Days 0 and 28 and Weeks 8, 13, 17, 21, 26, 32, 36, 40, 44, 48, and 52. Subjects with unresolved ISRs at Week 52 or who report a new ISR after Week 52 will be followed every 3 months through ISR resolution or Week 78, whichever comes first (adverse events and concomitant medication use will also be evaluated at post-week 52 visits, as relevant).

2.2. Randomization, Allocation Concealment, and Blinding

Subjects will be randomized in a 1:1:1:1 allocation ratio to one of the 3 TV-46046 test groups or the Depo-subQ 104 reference group, using a permuted block design stratified by investigational center. The randomization sequence will be developed by an FHI 360 programmer not otherwise involved in the study using a validated SAS/STAT® program (version 9.4). Randomized subjects who discontinue early will not be replaced. Additional details (including block sizes) are maintained in a separate document.

Allocation will be concealed using opaque, sequentially numbered randomization envelopes provided to each investigational center. Trained staff will open the next available envelope, and allocate the next treatment assignment, only after a subject has completed all other baseline procedures and is determined to be eligible for treatment. Randomization envelopes will be

¹ The study protocol defines day of treatment initiation as Day 0. Noting that the day of treatment initiation is defined as Day 1 in CDISC, protocol Day X will be mapped to treatment Day X+1 when creating ADaM data.

Statistical Analysis Plan Version 5.0

Pharmacokinetics Study–Healthy Subjects

Study TV46046-WH-10159

maintained in a secure location at each center, with access limited to authorized personnel per center-specific study procedures.

The study will only be partially blinded due to differences in appearance of the investigational products. Investigational center staff preparing and administering injections will not be blinded but will be trained to shield the syringe from view of the subject. FHI 360 and sponsor study team members involved in assessment of adverse events, data analysis, and results interpretation will be blinded to treatment assignment until the first interim analysis, after which time only investigational center staff assessing safety outcomes or performing subject interviews will remain blinded. Lab personnel performing MPA testing will remain blinded throughout the study. Emergency unblinding procedures for medical reasons are described in the study Pharmacy Manual and Safety Management Plan. Any instances of unscheduled unblinding will be described in the CSR.

2.3. Blinded Data Review

Prior to the first planned interim analysis, study data will be reviewed by the Coordinating Investigator and Lead Biostatistician or their designee(s) to inform analysis decisions. The Lead Biostatistician will be responsible for developing blinded listings for this review and will document the Coordinating Investigator's decisions prior to unblinding. These reviews will include (but not necessarily be limited to) important protocol deviations for inclusion/exclusion of subjects and/or data points from the primary analysis sets, assessment of potential outliers, and any necessary adjustments to imputation rules for missing MPA results due to out of window visits. Blinded data reviews may likewise occur to inform clinical queries to the site.

2.4. Interim Monitoring

A Study Review Committee (SRC) composed of FHI 360 and Sponsor staff will convene for one or more interim data reviews after at least 80% of treated subjects have had an opportunity to complete 7.5 months of follow-up. Unplanned reviews may be triggered by the occurrence of ISRs and/or serious and related adverse events as specified in the protocol and detailed in a separate SRC Operational Plan. The SRC may recommend that the trial be modified or halted to ensure the safety and well-being of study subjects at the time of any planned or unplanned interim analysis. There will be no adjustment to type I error or the coverage of confidence intervals (CIs) to account for interim reviews of data.

2.5. Sample Size and Power Considerations

There are no hypothesis tests in this phase 1 pharmacokinetics study, and the sample size was not based on formal power calculations. Rather, 60 treated subjects (15 per group) was determined to be sufficient to inform the selection of a dose of TV-46046 for future pivotal study based on the results of two recent trials of MPA products implemented under similar protocols. [REDACTED]

[REDACTED]

[REDACTED]

Statistical Analysis Plan Version 5.0

Pharmacokinetics Study–Healthy Subjects

Study TV46046-WH-10159

**2.6. Sequence of Planned Analyses****2.6.1. Planned Interim Analysis**

A planned review of interim data will occur when at least 80% of treated subjects have had an opportunity to complete 7.5 months of follow-up. This interim analysis is intended to inform the decision to move to - and the dose selection for - a future pivotal study. If recommended by the SRC, additional interim analyses of pharmacokinetic data may be performed in advance of an end of phase 2 meeting. Unplanned interim analyses for purposes of monitoring participant safety may be triggered by safety endpoints or otherwise made at the discretion of the SRC.

2.6.2. Final Analysis and Reporting

All final analyses will be performed after the last subject has completed the study. [REDACTED]

3. ANALYSIS SETS

3.1. Screened Analysis Set

The Screened Analysis Set will include all subjects who are screened for study participation, regardless of whether they are enrolled and randomized. In this analysis set, analyses will be performed according to enrollment status.

3.2. Randomized Analysis Set

The Randomized Analysis Set will include all randomized subjects, regardless of whether they received a dose of study drug. The Randomized Analysis Set will be used for assessment of subject disposition.

3.3. Safety Analysis Set

The Safety Analysis Set will be a subset of the Randomized Analysis Set, excluding any subject who failed to receive an injection of study drug. Subjects will be analyzed according to treatment received, regardless of any allocation errors. The Safety Analysis Set will be used for all assessments of baseline, safety, and acceptability data, as well as sensitivity analyses of pharmacokinetics data that include all treated subjects, regardless of any exclusions from the primary pharmacokinetics analyses.

3.4. Pharmacokinetic Analysis Set

The Pharmacokinetic Analysis Set will be a subset of the Safety Analysis Set, excluding any subjects who had a baseline MPA concentration that exceeded 5% of their individual Cmax, had an important protocol deviation that may affect interpretation of their MPA data, or failed to provide at least one evaluable post-treatment MPA specimen. The Pharmacokinetic Set will be analyzed according to treatment received. Failure to follow the intention-to-treat principle will be justified on the grounds that the study is not intended to make definitive conclusions regarding the efficacy of TV-46046.

A single intercurrent event (IcE) relevant to pharmacokinetic analyses is anticipated as possible for this study: the use of concomitant medications known to impact the pharmacokinetics of MPA (e.g. inducers or inhibitors of CYP3A4).² The strategy for handling this potential IcE is to exclude MPA results obtained during periods of relevant medication use (and assume that the excluded drug concentration data are missing completely at random) when defining estimands and constructing estimators based on non-compartmental analysis (NCA) methods. Additional details regarding the impact of IcEs on estimands and estimators are provided in Section 10.

² Intercurrent events typical to other studies, such as discontinuing treatment and treatment switching, are not relevant given that each subject is administered only a single dose of drug which can't be discontinued.

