- w. desires to become pregnant in subsequent 24 months
- x. has been pregnant in last 3 months
- y. is currently lactating
- z. is using or planning to use prohibited drugs per protocol in the next 12 months
 - aa. has known sensitivity to MPA or inactive ingredients
 - bb. plans to move to another location in the next 12 months
 - cc. has any condition (social or medical), which in the opinion of the investigator would make study participation unsafe, would interfere with adherence to the clinical study requirements or complicate data interpretation

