4.6. Prior and Concomitant Therapy or Medication

Any prior or concomitant medication a subject has had within 30 days before study drug administration and up to the final visit will be recorded as a concomitant medication on the appropriate CRF. During the four scheduled follow-up visits the investigator will ask subjects whether they have taken any medications, including over-the-counter medications, vitamins, or herbal or nutritional supplements, since the previous visit. During all other visits information on the use of concomitant medications will be documented only if self-reported by the subject. Generic or trade name, indication, route of administration, dosage, and start and end dates will be recorded.

The following medications should not be used during this study: aminoglutethimide; steroid hormones (estrogens, progestins and androgens); and antiretroviral drugs including non-nucleoside reverse transcriptase inhibitors (efavirenz and nevirapine) and ritonavir-boosted protease inhibitors. The use of prohibited drugs will be documented as an important protocol deviation. In addition, application of bandages to injection sites will be discouraged.

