9.1. Sample Size Determination and Rationale

The goal of the study is to select a dose of TV-46046 that is safe and well tolerated, and has a PK profile consistent with contraceptive protection when injected every 6 months. Recognizing that there is no formal hypothesis test on which to base same size calculations, 15 subjects per treatment group (approximately 60 in total) are expected to be sufficient to inform dose selection based on data from recent PK studies of MPA delivered subcutaneously. [REDACTED]

[REDACTED]

[REDACTED]

[REDACTED]

[REDACTED]

[REDACTED]

[REDACTED]

The intent of the study is to have a minimum of 54 subjects with evaluable data complete 32 weeks per protocol. Additional subjects may be enrolled to complete the minimum number of evaluable subjects at the discretion of the Sponsor. SRC will provide guidance regarding the value of expanding enrollment and size of such expansion to help ensure that at least 54 subjects complete 32 weeks per protocol.

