9.3.4. Pharmacokinetic Analysis Set

The Pharmacokinetic Analysis Set will be a subset of the Safety Analysis Set, excluding any subjects who had a baseline MPA concentration that exceeded 5% of their individual C_{max} , had an important protocol deviation that may affect interpretation of the MPA data, or failed to provide at least one evaluable post-treatment MPA specimen. The analysis set will exclude MPA data collected during time periods when subjects used a concomitant medication known to impact the pharmacokinetics of MPA. In this analysis set, subjects will be analyzed according to treatment received, regardless of any allocation errors.

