4.3. Handling of Withdrawals and Missing Data

4.3.1. Discontinuation and Missing Data

Subjects who are discontinued from the study after being randomized will not be replaced. All available data up to the time of discontinuation will be included in relevant analyses. Except as noted in Section 4.3.2, missing data will not be estimated or imputed.

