10.3. Intercurrent Events

A single IcE is anticipated as possibly occurring in this study: the use of concomitant medications known to impact the pharmacokinetics of MPA. Any MPA results obtained from a subject between the initiation date of a relevant medication and the last date that the medication may have impacted the pharmacokinetics of MPA will be excluded from the Pharmacokinetics Analysis Set. This strategy corresponds to the hypothetical scenario in which the IcE did not occur when defining pharmacokinetic estimands, and the corresponding estimators will be (asymptotically) unbiased under the assumption that the excluded data are missing completely at random (i.e., the reason for use of the medication is independent of the pharmacokinetics of MPA). The precise dates of exclusion will be adjudicated by the Lead Biostatistician and Clinical Investigator in blind review whenever possible. The impact of exclusions on pharmacokinetic parameter estimators are described further in Section 10.4.

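### Entry exclusions t and z screen for fewer drugs than the rule that removes MPA results, so a woman can be randomised who then adds nothing to the primary PK analysis

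*SAP*

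**What the plan says.** **Entry.** Protocol 3.2.2 exclusion z bars a woman who "is using or planning to use prohibited drugs per protocol in the next 12 months". Exclusion t looks back one month for the same prohibited drugs, and adds investigational drugs and several hormonal contraceptives. The prohibited list is in protocol 4.6: "The following medications should not be used during this study: aminoglutethimide; steroid hormones (estrogens, progestins and androgens); and antiretroviral drugs", with non-nucleoside reverse transcriptase inhibitors and ritonavir-boosted protease inhibitors given as instances of the last group. It does not mention CYP3A4 inducers or inhibitors as a class.

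**Analysis.** Protocol 9.3.4 says the PK set will "exclude MPA data collected during time periods when subjects used a concomitant medication known to impact the pharmacokinetics of MPA". SAP 3.4 has the same rule ("exclude MPA results obtained during periods of relevant medication use") and adds CYP3A4 drugs as an example when it names the triggering event: "the use of concomitant medications known to impact the pharmacokinetics of MPA (e.g. inducers or inhibitors of CYP3A4". SAP 10.3 defines the excluded period as running "between the initiation date of a relevant medication and the last date that the medication may have impacted the pharmacokinetics of MPA".

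**Target.** Protocol 9.1 states: "The intent of the study is to have a minimum of 54 subjects with evaluable data complete 32 weeks per protocol". About 60 women are planned, 15 per group.

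**The concern.** The criteria that decide who enters and the rule that decides whose MPA results count cover different sets of drugs. For a drug started unexpectedly after dosing, that is reasonable, because an intercurrent-event rule has to catch whatever is taken. For a drug already in use or planned at entry, the problem can be foreseen. The woman meets t and z, receives a single injection that cannot be withdrawn, and gives blood for a year. Her results are then set aside in the primary analysis. Protocol 9.5 says healthy subjects are recruited partly to avoid confounding by comedication, and the entry criteria do not fully deliver that. What is at stake is the number of women informing each arm of a small dose-selection study.

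**Working it through.** **1. The rules side by side**

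| Place | Use | Drugs covered |
|---|---|---|
| Protocol 4.6 | Prohibited during the study | Named drugs and groups |
| Protocol 3.2.2 t | Previous month | The 4.6 list, investigational drugs, listed hormonal contraceptives |
| Protocol 3.2.2 z | Current, or planned in next 12 months | The 4.6 list only |
| Protocol 9.3.4 | Removal of MPA data | Any drug known to affect MPA pharmacokinetics |
| SAP 3.4, 10.3 | Removal of MPA data | The same class, with CYP3A4 drugs as the example |

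The first three rows refer to stated drugs and groups. The last two describe an open class. The gap is any drug in that class that the first three rows do not cover.

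**2. What happens to a woman in the gap**

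- *Continuous use from before dosing.* The drug's start date precedes the injection, so the SAP 10.3 period covers every post-dose sample. Protocol Table 4 gives 32 MPA samples, one of them pre-dose, so 32 − 1 = 31 are excluded. With no usable post-dose sample she leaves the PK set under SAP 3.4 (taking an excluded result as not evaluable).
- *Use that stops early.* SAP 10.5 makes Cmax non-evaluable if such a drug was used before Cmax occurred. Tmax goes with it, and no AUC is reported when Cmax is not estimable. Concentrations at days 91, 182 and 210 could survive if the period of possible impact had ended.

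**3. Effect on precision**

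The plan has no power calculation to reproduce. SAP 10.6 specifies 90% t-based intervals on log-transformed values. With a common SD and a two-group comparison, the log-scale half-width is proportional to

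w(n₁, n₂) = t(0.95, n₁ + n₂ − 2) × √(1/n₁ + 1/n₂),

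and the SD cancels in the ratio to the full design.

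| Women left in test arm (reference 15) | w | Ratio to 15 v 15 |
|---|---|---|
| 15 | 0.6212 | 1.000 |
| 14 | 0.6330 | 1.019 |
| 13 | 0.6463 | 1.041 |
| 12 | 0.6616 | 1.065 |

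One, two or three women lost widen the interval by about 1.9%, 4.1% or 6.5%. The formula is symmetric, so one woman lost from the reference arm widens all three test/reference comparisons by 1.9%.

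**4. How many women?**

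The documents give no rate, so the rates below are assumptions. They take 60 women with no extra enrolment, and every user becoming non-evaluable. The margin is 60 − 54 = 6, so the target is missed at 7 or more (binomial).

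| Assumed rate | Expected users of 60 | Chance of ≥1 in an arm of 15 | Chance of ≥7 of 60 |
|---|---|---|---|
| 2% | 1.2 | 26% | <0.1% |
| 5% | 3 | 54% | 3% |
| 10% | 6 | 79% | 39% |

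**The case against.** The case against making much of this is strong in several places.

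- *Different rules in the two documents.* A reader might infer that the SAP removes data the protocol would keep. It does not. Protocol 9.3.4 has the same broad rule and the SAP adds only an example. The mismatch lies between the entry criteria and the removal rule, and it exists within the protocol itself.
- *Unrecoverable loss.* A reader might treat the margin of six as fixed, citing the SAP 4.3.1 statement: "Subjects who are discontinued from the study after being randomized will not be replaced". That rule concerns women who discontinue, and a woman on an interacting drug need not. Protocol 9.1 lets the sponsor enrol more women to reach 54, with Study Review Committee guidance. SAP 10.7 repeats the non-compartmental analysis on the Safety Set with nothing excluded, so her data are still analysed. What is lost is her contribution to the primary analysis.
- *Added bias.* A reader might infer greater reliance on the SAP's missing-completely-at-random assumption. Use already present at entry is a pre-randomisation characteristic. Dropping continuous users leaves a randomised comparison among non-users, the same women that screening would have enrolled. That assumption matters chiefly for drugs started after dosing.
- *Rarity.* Women must be healthy, and several chronic conditions are excluded. Rates towards 10% have no support in the documents.
- *Existing safeguards.* Exclusion cc mentions complicating data interpretation, but it is framed around a condition, depends on the investigator's opinion and compels nothing.

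The first four points limit the size of the concern. None closes the gap for current or planned use at entry.

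**Conclusion.** The gap is real and narrow. Exclusions t and z admit women whose current or planned medication will void their MPA results under protocol 9.3.4 and SAP 3.4, 10.3 and 10.5. The consequence is lost precision, about 1.9% on a descriptive 90% interval for each woman lost from an arm of 15. That figure assumes a common SD and a two-group t interval. The total effect depends on a rate of use that the documents do not give and that is probably low. At 2% to 5%, this cause alone would seldom breach the 54-woman target even without further enrolment. The validity of the primary comparison is not in question. This is a cheap improvement to the entry criteria.

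**What to change.** Reconcile exclusions t and z with protocol 9.3.4 and SAP 3.4 and 10.3, so that current or planned use at entry of a drug that would trigger removal of MPA results is checked at screening. The sponsor should choose the drugs and state them in one place to which both the entry criteria and the SAP refer. Because t and z now work by reference to the prohibited list, the link can be written as a separate entry clause. Whether the on-study list in 4.6 should change is a separate matter for the sponsor. Keep the broad removal rule for unplanned use after dosing.

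The cost is a protocol amendment to two criteria, a matching SAP reference and a slightly smaller eligible pool. No new procedure is needed: eligibility is reviewed at screening and on Day 0 (protocol Table 1), and medication from the 30 days before dosing is already recorded (protocol 4.6). The change helps only women not yet enrolled. SAP version 5.0 is dated February 2023 and its change log refers to the interim analysis, which was due once at least 80% of treated women could have completed 7.5 months. The benefit to this study may therefore be small, and the main use may be in the planned pivotal study.
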